All source data will be organized and entered onto RedCap (www.redcap.partners.org). Any pertinent notes to file regarding the subject and their study visit will be documented by the study coordinator and kept in the applicable subject-file on RecCAP. All subjects will be assigned a study identification number. We will pre-test/pilot test the source documents on RedCap prior to enrolling any subjects to ensure confidentiality and effectiveness. The source documents on RedCap will only be accessible to study staff by a special login/password. The surveys will be accessible by invitation only with a special login/password. RedCap documents will not be accessible to the public. There will be no bias to conducting research using RedCap because all surveys will be completed by the patient while he or she is at the study visit. We will use computers and internet at Wellman Center for Photomedicine for the completion of these documents.

This study will be performed in accordance with the Declaration of the World Assembly, 1975, Tokyo (Fed. Reg. 40, 16056, April 9, 1975) and the "Guiding Principles for Human Studies" of the Massachusetts General Hospital. These guidelines will be followed specifically with regard to the privacy and confidentiality of patient care and study records.

SENDING SPECIMENS/DATA TO RESEARCH COLLABORATORS OUTSIDE PARTNERS

Specimens or data collected by Partners investigators will be sent to research collaborators outside Partners, indicate to whom specimens/data will be sent, what information will be sent, and whether the specimens/data will contain identifiers that could be used by the outside collaborators to link the specimens/data to individual subjects.

N/A

Specifically address whether specimens/data will be stored at collaborating sites outside Partners for future use not described in the protocol. Include whether subjects can withdraw their specimens/data, and how they would do so. When appropriate, submit documentation of IRB approval from the recipient institution.

N/A

RECEIVING SPECIMENS/DATA FROM RESEARCH COLLABORATORS OUTSIDE PARTNERS

When specimens or data collected by research collaborators outside Partners will be sent to Partners investigators, indicate from where the specimens/data will be obtained and whether the specimens/data will contain identifiers that could be used by Partners investigators to link the specimens/data to individual subjects. When appropriate, submit documentation of IRB approval and a copy of the IRB-approved consent form from the institution where the specimens/data were collected.

N/A

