until the next skin cancer needs to be excised. The current treatment regimens for treating AKs and SCCs involve frequent office visits with extensive cryotherapy, numerous biopsies and excisions. We often use topical medications to treat field cancerization, such as 5-fluorouracil or imiquimod. These treatments are often ineffective and need to be repeated frequently. The need for multiple treatments may be related to compliance. Often people cannot tolerate these treatment regimens. Thus there is the need for an optimized treatment regimen to improve clearing the field of atypia and precancerous lesions. This would cut down on cost, risks of surgical procedures, and patient discomfort.

We want to evaluate of effectiveness of ablative carbon dioxide (CO2) laser used to precisely remove the epidermis of an entire field, thus removing all the typical keratinocytes and basal stem cells that have been mutated. After the CO2 treatment a portion of the area treated would then be covered with autologous epidermal skin grafts from a non-exposed area (buttocks or thigh). We hypothesize that the epidermal skin grafts would not only improve/hasten the wound healing process after CO2 but it would also provide the field with stem cells that have yet to receive damaging radiation.

Ablative CO2 laser was first used by surgeons to cut and vaporize tissue. It then became a popular device with both surgeons and dermatologists for treatment of deep facial rhytides. More recently these lasers have been used to treat significantly photodamaged skin and actinic keratoses. The studies showing varying rates of reduced AK counts over short periods of time. The longest follow up being 2 years.

Suction blister autologous epidermal grafting is a simple procedure being used most commonly for vitiligo, but also wound healing and scarring. There are several IRB approved protocols at MGH already using this technique (PI: [name], MPH).

RESEARCH DESIGN AND METHODS

Briefly describe study design and anticipated enrollment, i.e., number of subjects to be enrolled by researchers study-wide and by Partners researchers. Provide a brief summary of the eligibility criteria (for example, age range, gender, medical condition). Include any local site restrictions, for example, "Enrollment at Partners will be limited to adults although the sponsor's protocol is open to both children and adults."

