The proposed pilot study is a 3 year prospective, randomized, controlled comparison of a single treatment with carbon dioxide laser resurfacing vs. carbon dioxide resurfacing plus autologous epidermal skin graft from a non sun exposed site vs. control. Thirty subjects will receive treatment with each of the modalities on randomly-assigned portions of the treatment area. The primary measures of efficacy are (a) count of the number of actinic keratosis and non melanoma skin cancers, (b) blinded evaluation of severity from standard digital photographs taken before and after the treatments, and (c) change in histology before and after treatment: seen by grading and change of p53 immunostaining. Other study endpoints include time point to the next skin cancer is found in the treatment area, overall clinical appearance, change in mutant P53 of skin samples, and telomere length variability.

Safety measures include (a) pain, (b) scarring, (c) wound healing, (d) and infection

Subjects will be recruited through advertisements posted within the hospital(s), outpatient dermatology clinics and partners electronic mail.

Inclusion criteria

1. Subjects with ages between 18 and 85 years, male or female.
2. Subjects with at least 4 clinically diagnosed AKs per treatment site (up to 200 sq cm), excluding the face.
3. Subjects with history of at least 1 skin cancer within the past year
4. Willingness to participate in the study
5. Informed consent agreement signed by the subject
6. Willingness to follow the treatment schedule and post treatment care requirements
7. Willingness to not use topical or systemic (oral) TREATMENT medications including imiquimod, 5 Fluorouracil, photodynamic therapy, during the treatment period.
8. Has not had treatment for AKs in the treatment area for 4 weeks prior to enrollment

Exclusion criteria

1. Subjects with active skin cancer in the treatment area. Once the non-melanoma skin cancer has been treated, the subject can be immediately enrolled.
2. Infection of the area to be treated
3. An open wound in the area to be treated
4. Presence of suntan in the area to be treated, or active tanning during the study
5. Subjects who have taken medication known to induce photosensitivity in the previous 3 months
6. The patient has any contraindication to use of the CO2 laser
7. Subject is unable to comply with treatment, home care or follow-up visits
8. Subject is pregnant or breast feeding

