9. Prior use of topical retinoids, 5 fluorouracil, or imiquimod in treated areas within one month of initial treatment
10. Prior skin treatment with laser or other devices in the treated area within two months of initial treatment or during the course of the study;
11. Adverse reactions to compounds of any external agent (e.g., gels, lotions or anesthetic creams) required for use in the study, if no alternative to the said agent exists;
12. Concurrent inflammatory skin conditions, including, but not limited to, eczema, contact dermatitis of any severity;
13. Active Herpes Simplex at the time of treatment;
14. Multiple dysplastic nevi in area to be treated;
15. Having a bleeding disorder or taking anticoagulation medications, including heavy use of aspirin, in a manner which does not allow for a minimum 10 day washout period prior to each treatment (as per the patient's physician discretion);
16. Significant concurrent illness, such as uncontrolled diabetes, (i.e., any disease state that in the opinion of the Investigator would interfere with the anesthesia, treatment, or healing process);
17. Mentally incompetent, prisoner or evidence of active substance or alcohol abuse;
18. Any condition which, in the Investigator's opinion, would make it unsafe (for the subject or study personnel) to treat the subject as part of this research study.

Briefly describe study procedures. Include any local site restrictions, for example, "Subjects enrolled at Partners will not participate in the pharmacokinetic portion of the study." Describe study endpoints.

This study will be conducted at the Wellman Center for Photomedicine human studies facility at MGH. The first contact will be made in by the subject in response to the study advertisement. During this first study contact subjects will be informed regarding the goals of the study, inclusion/exclusion criteria, study procedure, potential benefits, risks and duration of the study. Subjects will be asked if they would like a copy of the consent form to read, either through the mail or email. Subjects who meet the inclusion and exclusion criteria and remain interested in the study will be invited for a screening visit.

The study involves 1 screening visit, 1 baseline/ treatment visit, and 10 study visits over a period of 3 years. Objective and safety assessments will be done at all treatment visits.

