Visit	Informed consent	Urine preg test	TX	Photo	# NMSC prior	AK/NMSC count	Biopsy	Overall Appearance scale	AE	Pain scale (VAS)	Patient side effect report	Inv wound assess
Screen	X											
Baseline/TX (Day 0)		X	X	X	X	X	X	X	X			
Day 3				X				X	X	X	X	X
Day 7				X				X	X	X	X	X
Week 4				X		X		X	X	X	X	X
3 month				X		X	X	X	X			X
6 month				X		X		X	X			
1 year				X		X		X	X			
1.5 – 2.5 year visits				X		X			X			
3 year				X		X	X	X	X			

Baseline/Treatment Visit 1(Day 0)

- Baseline and treatment can occur on separate days if necessary. These visits will occur within 2 weeks of each other if done separately**

Part I– Baseline Evaluations (lasting 1 hour).

Part II- Treatment (lasting 2.5 hours)

Part I– Baseline Evaluations (lasting 1 hour).

The investigator will determine the treatment area

- I. AK count within the treatment area**
- II. Confirm no clinically evident NMSC within the treatment area**
- III. Obtain history of number of skin cancers and locations. History will be taken orally from patient but will also review the medical records.**
- IV. Tracings of the treatment area and control site as needed to document**

V. Shave biopsy technique will be used to harvest epidermal biopsies for histologic assessment. 6 scouting biopsies will be done in the treatment area for histologic evaluation and immunostaining

VI. Baseline pre-treatment Photography of treatment area and control site

Shave biopsy for histology

Area will be prepped with alcohol swab, injected with Lidocaine 1% with or without epinephrine. Shave biopsy will be performed with a dermablade. Tissue samples will be taken to the lab and processed for immunostaining of p53 and PCR to determine telomere length. A portion will be frozen and backed for PCR analysis at the end of the study.

Part II- Treatment (lasting 2.5 hours)

- I) Urine pregnancy test for female not yet in menopause
- II) Subject will receive laser treatment to the treatment area. Topical anesthesia will be applied for 1 hour prior to the laser treatment.
- III) Epidermal suction blister graft harvest from donor site and application on randomized treatment area
- IV) Adverse event evaluation
- V) Patient assessments: pain

Procedures in more detail

Laser treatment

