- change in p53mutations
- change in telomere length

For studies involving treatment or diagnosis, provide information about standard of care at Partners (e.g., BWH, MGH) and indicate how the study procedures differ from standard care. Provide information on available alternative treatments, procedures, or methods of diagnosis.

Field cancerization and pre-skin cancers are currently treated through a number of ways including: spot treatment with cryotherapy, biopsy, excision; photodynamic therapy; or topical therapies, such as 5-fluorouracil, imiquimod, or ingenolmebutate. These treatments are often ineffective and need to be repeated frequently. The CO2 laser is another method for destruction of the epidermis. The hope is that this in office treatment would be effective as a single treatment. In addition, in office CO2 would be better controlled than at home treatments with topical creams or the spot treatment approach with cryotherapy, biopsy, or excision.

Describe how risks to subjects are minimized, for example, by using procedures which are consistent with sound research design and which do not unnecessarily expose subjects to risk or by using procedures already being performed on the subject for diagnostic or treatment purposes.

The CO2 laser has been used for many years and the standard of care for use is well established. All standard of care laser safety procedures will be followed (i.e. wearing appropriate eye protection) and all standard of care measures for prepping for a clean field will be taken minimize risk of infection. Will also review wound care instruction with patients and give them written instructions to take home.

Describe explicitly the methods for ensuring the safety of subjects. Provide objective criteria for removing a subject from the study, for example, objective criteria for worsening disease/lack of improvement and/or unacceptable adverse events. The inclusion of objective drop criteria is especially important in studies designed with placebo control groups.

There is only one treatment for this protocol. Safety data will be collected at each visit of the study. We will ensure that the patients continue to have regular dermatologic care. This study will not interfere with treatment of future skin conditions.

FORESEEABLE RISKS AND DISCOMFORTS

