Describe the plan to be followed by the Principal Investigator/study staff for review of adverse events experienced by subjects under his/her care, and when applicable, for review of sponsor safety reports and DSMB reports. Describe the plan for reporting adverse events to the sponsor and the Partners' IRB and, when applicable, for submitting sponsor safety reports and DSMB reports to the Partners' IRBs. When the investigator is also the sponsor of the IND/IDE, include the plan for reporting of adverse events to the FDA and, when applicable, to investigators at other sites.

NOTE: In addition to the adverse event reporting requirements of the sponsor, the principal investigator must follow the Partners Human Research Committee guidelines for Adverse Event Reporting

Any adverse events will be reviewed and analyzed by the Principal Investigator as soon as the event occurs and will be documented on Redcap. Any unanticipated problems involving risks to subjects or others including adverse events will be reported to the PHRC in accordance with PHRC unanticipated problems including adverse event reporting guidelines.

Patients will receive only one study treatment (visit 0). After that, no test site will receive study treatment (follow-ups). The patients will continue to have routine dermatologic care. If a pre-skin cancer, skin cancer, or other dermatologic disease develops within the treatment area or the control it will be treated with the standard of care by either the patient's dermatologist or the investigators of this study. Our study documents will note all treatments that are needed in the treatment area and the control. We expect that the control sites will not improve as much as treated sites, and they will serve also as a comparative endpoint.

MONITORING AND QUALITY ASSURANCE

Describe the plan to be followed by the principal investigator/study staff to monitor and assure the validity and integrity of the data and adherence to the IRB-approved protocol. Specify who will be responsible for monitoring, and the planned frequency of monitoring. For example, specify who will review the accuracy and completeness of case report form entries, source documents, and informed consent.

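### The bar on imiquimod, 5-FU and PDT runs for an undefined treatment period, and AKs cleared by permitted outside care leave the primary count, which pulls the laser-control difference toward zero

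*Protocol*

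**What the plan says.** Inclusion criterion 7 asks for "Willingness to not use topical or systemic (oral) TREATMENT medications including imiquimod, 5 Fluorouracil, photodynamic therapy, during the treatment period". The protocol uses the phrase *treatment period* nowhere else and gives it no start or end.

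On the number of treatments, the paragraph on ensuring subject safety says "There is only one treatment for this protocol". The adverse event part of Data and Safety Monitoring places that treatment at visit 0 and calls everything afterwards follow-up.

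Two exclusion criteria touch the same therapies. Item 9 excludes "Prior use of topical retinoids, 5 fluorouracil, or imiquimod in treated areas within one month of initial treatment", which looks only backwards. Item 10 excludes prior treatment with "laser or other devices in the treated area within two months of initial treatment or during the course of the study". It might reach PDT as a device, but only in the treated area. The baseline evaluations name the control separately: "Tracings of the treatment area and control site as needed to document".

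On care during follow-up, the adverse event section says that routine dermatologic care continues and that a new pre-cancer or cancer in the treatment area or the control receives standard of care. The study will note such treatments. The standard-of-care section lists cryotherapy, biopsy and excision, and also "photodynamic therapy; or topical therapies, such as 5-fluorouracil, imiquimod, or ingenolmebutate". The background adds "We often use topical medications to treat field cancerization, such as 5-fluorouracil or imiquimod". The safety paragraph says the study leaves later treatment of skin conditions unaffected.

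On measurement, primary measure (a) is the count of AKs and non-melanoma skin cancers, with AKs counted at examination. From week 4 the visits also ask about dermatologist visits and treatments given, and from month 3 this is checked against medical records.

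**The concern.** A count made by examination shows the AKs present that day. An AK frozen or cleared by a 5-FU course since the last visit is absent from it, just as if it had never arisen. The aim is to compare what the laser does with what happens under a control described in Aim 2 as no intervention. If outside care clears AKs on the control, the control looks better than untreated skin would.

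The two sides are unlikely to be affected equally. The protocol itself expects the control to improve less, so it will probably have more to treat. The distortion then runs one way, toward no difference. Noting that a treatment took place shows that the distortion occurred but does not measure it, because the plan does not ask how many AKs were treated or on which portion.

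**Working it through.** **Step 1. Visits and counts.** The protocol states 10 visits after baseline/treatment: Day 3, Day 7, week 4, months 3 and 6, and years 1, 1.5, 2, 2.5 and 3. That is 10, as stated. The visit table marks no AK count on Day 3 or Day 7, so 10 − 2 = 8 post-treatment AK counts remain.

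**Step 2. Counts covered by criterion 7, by end of the treatment period.**

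| Period ends | AK counts covered |
|---|---|
| Day 0 | 0 of 8 |
| Day 7 (end of wound care) | 0 of 8 |
| Week 4 | 1 of 8 |
| Month 3 | 2 of 8 |
| Year 3 | 8 of 8 |

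Only a whole-study reading covers all eight. That reading sits badly with the statement that later skin treatment is unaffected, and with the unqualified offer of standard of care. Where the protocol means the whole study it says so, as in exclusions 4 and 10.

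**Step 3. Illustration of size. All inputs here are assumed; none is in the protocol.** Let the mean AK count be 4 on control and 1 on laser, a true difference of 3.0. A share f of subjects has a field course that clears a fraction c of visible AKs.

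- Control only: 4 × (1 − f·c) − 1.
- Both portions alike: 3 × (1 − f·c).

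| f, c | Control only | Both portions |
|---|---|---|
| 0.10, 0.50 | 2.80 | 2.85 |
| 0.25, 0.75 | 2.25 | 2.44 |
| 0.50, 0.90 | 1.20 | 1.65 |

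Equal use on both portions shrinks the absolute difference but keeps the 4:1 ratio. Control-only use distorts both.

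**Step 4. Spot treatment has the same effect.** If a share s of AKs is spot-treated on both portions, the visible difference is 3 × (1 − s): 2.25, 1.5 and 0.3 for s = 0.25, 0.50 and 0.90. If each treated AK is added back once, the difference is 3.0 again, whatever s is.

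**Step 5. Power, as illustration only.** Assumptions: 30 subjects, one count per portion, Poisson counts with a shared gamma frailty (shape 1) and a portion-level gamma (shape 2), and a two-sided paired t-test at 5%. The three columns are the three rows of Step 3.

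| Means | No use | Control only | Both portions |
|---|---|---|---|
| 4 and 1 | 97% | 95%, 82%, 26% | 96%, 93%, 76% |
| 4 and 2 | 57% | 49%, 24%, 4% | 56%, 49%, 33% |

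The results depend heavily on the assumed spread. With milder variation (gamma shapes 4 and 8) and means 4 and 1, the middle control-only case gives 99% and the extreme one a little under 60%.

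**The case against.** **The wording may mean more than Day 0.** A promise to avoid drugs during a single session is nearly empty, so a longer window may be intended. The protocol is also loose with the word *treatment*: it speaks of assessments at all treatment visits, and of an initial treatment, although there is only one. This stands. A reader might infer that criterion 7 definitely lapses on Day 0, or that the protocol deliberately admits field therapy on the control. The text does not establish either. What it does establish is that no window is given and that none of the eight counts is clearly covered.

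**Routine care is deliberate and recorded.** This also stands. Subjects had a skin cancer within the past year, and withholding care would be wrong. A statistical analysis plan, not shown here, may also set rules for treated lesions. But it cannot recover the number of AKs treated on each portion if the visits do not collect it.

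**Field therapy may be the smaller route.** This is correct: by Step 4, heavy spot treatment removes more of the visible difference than the worst field-therapy case. Defining the period alone would therefore leave much of the problem, so the counting rule has to come first.

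**The large losses need control-only use.** Also correct. If the portions adjoin, a field course may cover more than one. The background calls these topicals often ineffective and poorly tolerated, which fits badly with 50% use and 90% clearance.

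**Conclusion.** The point holds as a gap in both the restriction and the count. The window in criterion 7 is undefined, standard care of every kind stays open on the control for 3 years, and AKs removed by that care disappear from part of a primary measure. The likely direction is toward no difference, on the inference that the control will need more treatment.

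The amount is unknown. It is small if outside treatment is rare, and less damaging if use is alike on all portions, since the ratio then survives. It is large only if use is frequent, effective and concentrated on the control, or if spot treatment removes most AKs before they are counted.

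A reader might take the simulated figures to mean that the trial loses most of its power. They do not show that: means, spread, usage, clearance and test are all assumed, only one of eight counts is modelled, and the pilot makes no power claim.

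**What to change.** 1. **Count what was treated.** In the follow-up visit lists and the adverse event section, record at each follow-up the number of AKs treated since the last visit, by date, modality and portion (laser, laser plus graft, control). Add each once to that portion's cumulative AK count, and report this beside the visible count. A treated AK that is still visible counts once.
2. **Give criterion 7 a window.** Replace the undefined period with Day 0 to the 3-year visit, limited to elective field therapy on the three study portions. State that lesion-directed care (cryotherapy, biopsy, excision) and any field therapy judged medically needed are always allowed and recorded. Refer to this rule in the safety paragraph and the adverse event section so that the three places agree.

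Both parts are needed. The cumulative count restores AKs that were seen and treated, but it cannot restore those that a field course prevented. Ingenol mebutate need not be added, because criterion 7 gives its drugs as examples of a wider class.

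**Cost.** One data field, filled from the history and record review already planned; a copy of the tracing for the treating dermatologist, since outside records may not name the portion; and a matching consent sentence. No visits are added. Some subjects would defer elective field therapy on up to 200 sq cm for up to 3 years. No medically needed care is withheld.

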- II) Exam of the treatment area: AK count, evaluate for clinically appearing NMSC present; evidence of scarring, evidence of infection; evidence of healing . Also will get history from patient: visits to dermatologist? and treatments rendered? Will also review medical records to confirm the history.
- III) 6 scouting epidermal biopsies, using shave biopsy technique (from the treatment area) for histology and immunostaining. Will also bank a portion for PCR at the end of the study.
- IV) Adverse event evaluation
- V) Investigator assessments: wound assessment, overall clinical appearance

Follow-up Visits(6 months, 1 year, 1.5 year, 2 year, 2.5 year) (lasting 30 minutes each)

- I) Photography
- II) Exam of the treatment area: AK count, evaluate for clinically appearing NMSC present; evidence of scarring, evidence of infection; evidence of healing . Also will get history from patient: visits to dermatologist? and treatments rendered? Will also review medical records to confirm the history.
- III) Adverse event evaluation
- IV) Investigator assessments: overall clinical appearance

End of Study visit (3 year) (lasting 1.5 hours)

Patients will exit the study after 3 years

- II) Photography
- III) Exam of the treatment area: AK count, evaluate for clinically appearing NMSC present; evidence of scarring, evidence of infection; evidence of healing . Also will get history from patient: visits to dermatologist? and treatments rendered? Will also review medical records to confirm the history

- IV) **6 scouting epidermal biopsies, using shave biopsy technique (from the treatment area) for histology and immunostaining. Will also bank a portion for PCR at the end of the study.
- V) Adverse event evaluation
- VI) Investigator assessments: overall clinical appearance

** During the course of the study, the subjects will have a total of 18 scouting epidermal biopsies using the shave biopsy technique

Evaluation of Safety and Efficacy

Assessed by investigators (non-blinded) and by blinded evaluators (clinical photographs), periodically for 3 years after a single treatment session.

Reported by the Patients

Specific form is attached.

I. Side effects reported by the patient:

To assess major and minor side-effects, patients will be asked for each treatment site to fill in the following sentence for each test site: **“The side effects I experienced after the treatment were:”** E.G.

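### The visit procedures name a control site at baseline and mention randomisation only for the graft, so they do not deliver the random assignment of all three portions that the design section promises

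*Protocol*

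**What the plan says.** **Design statement.** Research Design and Methods describes a randomised comparison of laser, laser plus graft, and control: "Thirty subjects will receive treatment with each of the modalities on randomly-assigned portions of the treatment area".

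**Part I (Baseline/Treatment Visit 1).** It opens with "The investigator will determine the treatment area". Item I is "AK count within the treatment area". Item IV is "Tracings of the treatment area and control site as needed to document", and item VI is "Baseline pre-treatment Photography of treatment area and control site".

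**Part II.** Item II applies the laser to the treatment area and excludes no part of it. Item III reads "Epidermal suction blister graft harvest from donor site and application on randomized treatment area". This is the only mention of randomisation in the visit procedures.

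**Timing.** "Baseline and treatment can occur on separate days if necessary"; if they are split, the two parts fall within 2 weeks of each other.

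**Blinding.** Under Evaluation of Safety and Efficacy, outcomes are "Assessed by investigators (non-blinded) and by blinded evaluators (clinical photographs), periodically for 3 years after a single treatment session".

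**The concern.** Each subject is their own control, so the unit that is randomised is a patch of skin. Random assignment protects the comparison only if the patches are drawn first, without anyone knowing which will be the control, and the assignment is revealed afterwards. If the control patch is picked by judgement, or its border is drawn by someone who knows that it is the control, it can start with more or fewer AKs, or with more or less damaged skin, than the lasered patches.

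Baseline AK burden is likely to carry into later AK counts. Part of a control-versus-laser difference in primary measure (a) could then reflect how the skin was divided. This is the contrast behind Specific Aim 1 and behind the comparative use of the control sites described under Data and Safety Monitoring. Part I also lists no separate AK count for the control site, so a starting difference might not be visible in the data.

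**Working it through.** The Protocol states no figure on this point, so there is none to reproduce. The check is mainly a comparison of sections, followed by an illustration under assumed values.

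**Step 1. Compare the sections.**

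| Question | Research Design and Methods | Visit procedures |
|---|---|---|
| What is randomised? | All modalities, on portions of the treatment area | Graft placement only (Part II item III) |
| Where is the control? | One of the three compared arms, so implied to be a portion of the treatment area | Named apart from the treatment area (Part I items IV and VI) |
| What is lasered? | Assigned portions | The treatment area, with nothing held out (Part II item II) |
| When is the assignment drawn? | Not stated | Not stated |

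The Background section fits the second column of answers better than the first: it describes grafts covering a portion of the lasered area. That suggests a lasered field split for grafting, with the control elsewhere.

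**Step 2. Consider when the draw could happen.** A site cannot be traced and photographed as the control unless somebody has already designated it.

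- If the assignment is drawn before the tracing, a non-blinded investigator may be outlining the control with its status known. No step requires unlabelled portions to be fixed first.
- If the assignment is drawn in Part II, the control was named before the draw. It was then chosen rather than randomised, contrary to the design section.

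Either way, control-versus-treated status is known at the tracing and photography steps.

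**Step 3. Baseline count.** Item I covers the treatment area. The control site first appears in item IV. No count by portion, and none for the control site, is listed in Part I.

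**Step 4. Illustrative size, for the case of a chosen control only.** Assumptions, none from the Protocol: N AKs fall at random over three equal portions. The control is the portion with most AKs in a share f of subjects, and is random otherwise.

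- D = E[max] − (N − E[max])/2, the expected excess of the fullest portion over the mean of the other two.
- Baseline bias = f × D, expressed as a share of the mean count per portion, N/3.

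By hand for N = 4, the splits (4,0,0), (3,1,0), (2,2,0) and (2,1,1) have probabilities 3/81, 24/81, 18/81 and 36/81. So E[max] = (12 + 72 + 36 + 72)/81 = 2.37, and D = 2.37 − 1.63/2 = 1.56. The other rows come from the same exact enumeration.

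| N | E[max] | D | f = 10%: AKs (share of N/3) | f = 25%: AKs (share of N/3) |
|---|---|---|---|---|
| 4 | 2.37 | 1.56 | 0.16 (12%) | 0.39 (29%) |
| 12 | 5.73 | 2.60 | 0.26 (6%) | 0.65 (16%) |
| 20 | 8.89 | 3.33 | 0.33 (5%) | 0.83 (12%) |

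Choosing the portion with fewest AKs as control gives a bias of similar size in the other direction: 25%, 15% and 12% at f = 25%.

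**The case against.** The strongest reply is that the Protocol never says the allocation is known when borders and counts are made. Most of its parts stand.

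- **The draw is not dated.** Part II item III describes where the graft goes, not when the assignment is made. A reader might infer that it is the only randomisation step and that the baseline work precedes it by up to 2 weeks. The text does not support that: the draw could come earlier, and separate days are optional.
- **Only one contrast is affected.** At most, control-versus-treated status is known in Part I. Nothing shows that laser versus laser plus graft is known then.
- **The count may precede the designation.** Item I is listed before the control is first mentioned. A reader might infer that baseline counts are made with the allocation known, but the list does not show this. Nor does it prevent it.
- **The illustration is limited.** It models choice of the control patch, not shaping of borders, and f has no source. The row for N = 4 may be impossible: inclusion criterion 2 requires at least 4 AKs per treatment site, and the appearance form labels the laser and the laser-plus-graft areas as separate treatment sites, which would mean at least 8 AKs on lasered skin alone.
- **Baseline adjustment could help.** It is commonly left to a statistical analysis plan, which is not shown. But it needs a count for each portion, and Part I lists none for the control. It would also not correct differences in skin damage that the count does not capture.

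The reply does not remove the conflict between the two sections. The tracing and labelling of skin areas is a visit procedure that this Protocol itself sets out, so an analysis plan would not repair it.

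**Conclusion.** The concern holds in a limited form. The design section promises random assignment of all three modalities to portions of the treatment area, and the visit procedures do not deliver it for the control. Followed as written, they leave the control patch either chosen by the investigator or outlined with its status known, with no listed baseline AK count. The control-versus-laser comparison in primary measure (a) is therefore open to selection bias, in either direction.

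The risk is an inference from the written sequence. The Protocol does not state that concealment is broken, and no bias is shown to have occurred.

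The size is unknown. Under the assumptions of step 4, a baseline excess of about 5–16% of the mean count per portion is plausible for 12–20 AKs in the field. It would be 12–29% for 4 AKs, if criterion 2 allows so few. These figures illustrate scale and are not estimates.

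**What to change.** Reconcile Research Design and Methods with the visit procedures, and state the order of steps.

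1. **Part I, items I, IV and VI.** The investigator outlines the whole field and divides it into three portions labelled A, B and C. Each is traced, photographed and AK-counted under its label, and the data are entered in REDCap.
2. **Start of Part II.** Only then is a pre-made, concealed assignment of all three portions revealed, from REDCap or from sealed envelopes held by someone other than the treating investigator.
3. **Part II, items II and III.** Reword so that laser and graft go to their assigned portions and the control portion is left without intervention, as the design section implies.

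If the control is meant to lie outside the treatment area, the design section should say so and state how that site is selected.

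Cost: wording, the order of existing steps, and a prepared list in a database already in use. No visit or procedure is added, and no added staff should be needed provided that someone other than the treating investigator can hold the list. The downside is a few minutes per subject to count each portion and open the assignment.
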